21.7.1.2 Secondary Endpoints

There are 4 secondary endpoints of interest in this study. No adjustments for multiple comparisons/testing will be performed for the other secondary endpoints. Analyses will be based on the observed data using the FAS.

The secondary endpoints are:

- Hb increment
 - Calculation: $[(\text{post-transfusion Hb} - \text{pre-transfusion Hb})/\text{Hb transfused}]/\text{RBC volume in subject at pre-transfusion}$
 - Hb transfused in the above formula is the sum of Hb content of each unit transfused calculated as $(\text{Hb/dL} \times \text{volume})/100$
 - Note: RBC volume in subjects at pre-transfusion is based on weight, height, sex, and pre-transfusion Hct. Example formulas are provided below where weight is in pounds and height is in inches.

$$\text{RBC Volume (Male)} = [(0.006012 \times \text{height}^3)/(14.6 \times \text{weight}) + 604] \times (\text{Hct}/100)$$

$$\text{RBC Volume (Female)} = [(0.005835 \times \text{height}^3)/(15 \times \text{weight}) + 183] \times (\text{Hct}/100)$$

- Actual Hb level post-transfusion (15 min)
- Proportional decline in post-transfusion Hb level
 - Calculation: $[(\text{Hb (t0)} - \text{Hb(t1)})/\text{Hb(t0)}]/\text{time between transfusion (days)}$
- RBC mass infused (volume x Hb/unit)

Two analyses will be carried out for the 15 minute Hb value. The first is directed at estimating the difference between the MIR RBC and REF RBC products and for this the mixed-effect model used for the primary outcome will be adopted to model the 15 minute Hb value as the response. A 95% confidence interval for the estimated mean difference in the 15 minute Hb value

will be computed. A second analysis will simply report the proportion of 15 minute Hb values within the pre-specified range of plus or minus 15% of the target value. This target value is specified at the start of follow-up and should remain fixed during the course of the study. This success rate will be estimated using generalized estimating equations with this binary response, a logistic link, a main effect for product type (MIR vs. REF RBCs) and an exchangeable correlation matrix to accommodate the dependence within patients. The resulting estimates will be provided as supplementary information to help in the interpretation of the primary analyses. There will be no non-inferiority bound or formal tests associated with these event rates.

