10.3 Off-Protocol Transfusions

Off-protocol transfusions are defined as any RBC transfusions other than those to which the subject was randomized (MIR RBCs or REF RBCs), regardless of the indication or reason for the transfusion. Following the off-protocol transfusion, the subject will continue to receive transfusions according to the allocated treatment arm and will continue study participation.

For each off-protocol transfusion, if possible, all of the same data as for protocol specified transfusions will be captured in the eCRF, including the indication and reason for the off-protocol transfusion and any modifications to the RBC product.

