14.3 With Each RBC Transfusion Episode

The following procedures will be completed before, during, and after each study transfusion unless otherwise noted. These procedures will be completed for all transfusions occurring during the 50 -day wash-in period plus the subsequent 2 transfusion episodes (for endpoint assessment) during each of the 2 crossover treatment periods. The date and time of transfusion, number of units, and type of product transfused will be documented in the eCRF. For off-protocol RBCs transfusion, the following characteristics will also be collected: transfused volume, type of RBC unit (per ISBT code), and hematocrit (if known).

Visits on 1 Day Post Transfusion and 7 Days Post Transfusion may be conducted in the clinic or may utilize a remote nursing visit.

At Baseline the Investigator will identify and document the target post-transfusion (15 min) Hb level; with each transfusion episode, the Investigator will perform the following:

1. Calculate the volume of RBCs required to achieve the target Hb (identified at baseline)
 - a. $[(\text{desired hemoglobin}) - (\text{current hemoglobin})] \times (\text{body weight [kg]}) \times (3/\text{Hct of RBC units}) = \text{mL to transfuse}^{39}$

Note: 3 is constant in the formula above
2. If the post-transfusion (15 min) Hb is under 15% of the target Hb, then an additional transfusion should be considered. If the post-transfusion Hb is over 15% of the target Hb, this will be documented^{39,40}

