21.1 Analysis Sets

21.1.1 Full Analysis Set

The Full Analysis Set (FAS) will include all randomized patients who have at least 1 normalized Hb AUC measurement. Patients will be analyzed according to the treatment (MIR RBCs, REF RBCs) to which they were to receive in each period as assigned at randomization.

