If a patient randomized to receive RBCs derived from Mirasol-treated WB in a particular period receives 2 successive off-protocol transfusion episodes (i.e., untreated RBCs) after completing the 50-day wash-in period, the primary endpoint for that period will be excluded from the analysis. If only 1 of the 2 successive transfusion episodes after the 50-day wash-in period is per protocol, only the primary endpoint associated with the per protocol transfusion episode will be analyzed. If at least 1 off-protocol transfusion occurs during a transfusion episode, the transfusion episode will be considered off-protocol. No off-protocol transfusions will be used for the primary analysis to minimize bias towards non-inferiority. The study will be executed to eliminate or minimize the risk of off-protocol transfusions.

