## **C. Secondary Efficacy Endpoints Analyses**

Hb increment, proportional decline in post-transfusion Hb and RBC mass infused will each be analyzed separately with a mixed effects repeated measures model fitting fixed effect terms for treatment, period and treatment\*period interaction. Subject will be included in the model as a random effect. The point estimates and associated 95% confidence intervals will be presented for the treatment differences.

Two analyses will be carried out for the 15 minute Hb value.

- The first is directed at estimating the difference between the MIR RBC and REF RBC products and for this the mixed-effect model used for the primary outcome will be adopted to model the 15 minute Hb value as the response. A 95% confidence interval for the estimated mean difference in the 15 minute Hb value will be computed.
- A second analysis will report the proportion of 15 minute Hb values within the pre-specified range of plus or minus 15% of the target value. This target value is specified at the start of study and should remain fixed during the course of the study. This success rate will be estimated using generalized estimating equations with this binary response, a logistic link, a main effect for product type (MIR vs. REF RBCs) and an exchangeable correlation matrix to accommodate the dependence within patients. The resulting estimates will be provided as supplementary information to help in the

interpretation of the primary analyses. There will be no non-inferiority bound or formal tests associated with these event rates.

All secondary endpoints will be descriptively summarized by treatment. Additionally, Hb increment, proportional decline in post-transfusion Hb and RBC mass infused will be presented graphically.

As a secondary analysis, actual Hb AUC will also be analyzed similarly to the primary endpoint described in Section VIII.B. Specifically, the Hb AUC will not be normalized to the 15-minute post-transfusion Hb level in this analysis.

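### The secondary mixed models count conventional RBCs given in a Mirasol period as Mirasol, which shrinks the product difference in Hb increment and, approximately, in proportional decline

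*Protocol*

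**What the plan says.** **Secondary endpoints.** Protocol 21.7.1.2 lists Hb increment, 15-minute post-transfusion Hb, proportional decline in Hb and RBC mass infused, and adds: "Analyses will be based on the observed data using the FAS". SAP VIII.A repeats this. The FAS (Protocol 21.1.1, SAP VI.I) attributes data to the product "to which they were to receive in each period as assigned at randomization". SAP VIII.C analyses Hb increment, proportional decline and RBC mass with mixed models "fitting fixed effect terms for treatment, period and treatment\*period interaction", and borrows the primary model for 15-minute Hb. None of this text contains an off-protocol rule.

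**Primary endpoint.** Protocol 21.7.1.1 drops primary values from a MIR period that come from off-protocol transfusions. SAP VIII.A makes a whole episode off-protocol if any transfusion in it was, and states: "No off-protocol transfusions will be used for the primary analysis to minimize bias towards non-inferiority".

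**Per-protocol set.** Protocol 21.1.3 and SAP VI.I plan it for the primary efficacy endpoint only.

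**What happens off protocol.** Under Protocol 10.3, any RBC transfusion other than the randomized product is off-protocol. Afterwards "the subject will continue to receive transfusions according to the allocated treatment arm and will continue study participation", and, if possible, "all of the same data as for protocol specified transfusions will be captured in the eCRF".

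**The concern.** Read together, these sections put conventional blood given in a MIR period into the secondary mixed models under the MIR label. No planned secondary analysis takes it out. The SAP recognises this bias and removes it from the primary analysis, but gives no reason for leaving it in the secondaries.

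Hb increment and proportional decline describe how the transfused product performs, and readers will use them to interpret the primary result. Protocol 21.7.1.2 also says that the first 15-minute Hb analysis is meant to estimate the difference between the two products. As-assigned data answer another question: what happens when a patient is allocated to MIR and sometimes receives conventional blood. Both questions are legitimate, but only the second is planned for the secondaries, and where conventional blood replaces MIR its answer makes the products look more alike.

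**Working it through.** The plan gives no off-protocol rate and no target figure for any secondary endpoint, so there is no planned figure to reproduce. The sample size of 77 (97 randomized) concerns the primary endpoint and does not change.

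**1. Attenuation when conventional blood replaces MIR.** Let M and R be the true means of an endpoint for MIR and REF episodes, and f the fraction of MIR-period episodes given wholly as conventional RBCs. Assume that such an episode behaves like REF, that REF periods are uncontaminated, and that off-protocol use is unrelated to the outcome.

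- Observed MIR mean = (1 - f)M + fR
- Observed difference = (1 - f)M + fR - R = (1 - f)(M - R)

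The relative difference, (M - R)/R, scales by the same factor.

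**2. Numbers.** As a stand-in for Hb increment, take the mean recoveries in Protocol 19.3.3, 82.5% for Mirasol-treated and 91.7% for untreated RBCs: 82.5/91.7 - 1 = -10.0%. The values of f are assumed.

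| f | Factor (1 - f) | Difference shown |
|---|---|---|
| 0% | 1.00 | -10.0% |
| 5% | 0.95 | -9.5% |
| 10% | 0.90 | -9.0% |
| 20% | 0.80 | -8.0% |

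Under the same assumptions, excluding the off-protocol episodes restores -10.0%.

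**3. Proportional decline.** The factor is only approximate. The measured fall in Hb comes from all circulating cells, including MIR cells from earlier transfusions, so one conventional episode does not turn the interval into a pure REF interval.

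**4. 15-minute Hb.** Protocol 14.3 calculates the volume needed to reach a fixed target Hb and has an additional transfusion considered when the 15-minute value is low. Dosing to a target can offset a product difference, so the formula in step 1 does not fix the direction or size of the shift.

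**5. RBC mass infused.** Assume 2 units per episode at 52.37 g Hb each (untreated units at 21 days, Table 19-5), and a MIR requirement of 1/0.833 of the REF mass (from the 16.7% reduction in Protocol 21.8).

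- REF mass: 2 x 52.37 = 104.74 g. MIR mass: 104.74/0.833 = 125.74 g. Difference: +21.0 g.
- At f = 10%, full replacement: 0.90 x 21.0 = +18.9 g, toward zero.
- At f = 10%, one conventional unit added: 21.0 + 0.10 x 52.37 = +26.2 g, away from zero.

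The direction therefore depends on whether the conventional unit replaces MIR or is added to it.

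**The case against.** **As-assigned analysis is legitimate.** It respects randomization. Excluding episodes that needed conventional blood conditions on something that happened after randomization, and can delete poor Mirasol results. This stands, and is why the exclusion analysis belongs beside the as-assigned one and should not replace it.

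**The effect may be small and visible.** SAP VIII.A says that the study will be run to keep off-protocol transfusions to a minimum, and SAP VIII.C reports their patterns and frequencies. At f = 5% the shift is half a percentage point on a 10% difference. The secondaries have no non-inferiority margin and no multiplicity control. All of this stands. But a frequency table does not give the product contrast with those episodes removed.

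**The borrowed primary model might bring its exclusion with it.** For 15-minute Hb, SAP VIII.C adopts the primary model. That settles the model terms; the data set is defined separately as observed FAS data. The objection does not stand.

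Three stronger readings are tempting, and the documents do not support them:

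- *Every secondary difference is pulled toward zero.* Steps 4 and 5 show that this does not follow for 15-minute Hb or RBC mass.
- *The success rate counts conventional blood as a Mirasol success.* The model for values within 15% of target uses *product type*, whereas the off-protocol frequency model says *assigned treatment*. The first may already mean product received. What is established is that the term is undefined.
- *Hb increment is inflated because an off-protocol unit is left out of the denominator.* Hb transfused is defined as a total over every unit given, and Protocol 14.3.1 and 16.1.1 require a CBC with Hb on each unit. The list in Protocol 14.3 for off-protocol units is in addition to this. Nothing tells the analyst to drop a unit.

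**Conclusion.** The gap is real and limited. The off-protocol exclusion stops at the primary endpoint, so the secondary mixed models attribute conventional blood in MIR periods to MIR, and no planned secondary analysis checks the effect. For Hb increment, and approximately for proportional decline, the MIR-REF difference shrinks by about f when conventional blood replaces MIR: from -10.0% to between -9.5% and -8.0% at an assumed f of 5% to 20%.

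That range rests on full replacement, on contamination in MIR periods only, and on recovery of autologous cells in healthy volunteers as a loose stand-in for Hb increment in thalassemia patients. Contamination mainly in MIR periods is plausible, because REF units come from routine inventory (Protocol 13.2) while MIR units need dedicated production and expire within 21 days; but it is an inference. For 15-minute Hb and RBC mass infused, no direction can be claimed. The point affects interpretation of the secondary endpoints, not the primary conclusion.

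**What to change.** In Protocol 21.7.1.2 and SAP VIII.C:

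1. For Hb increment, proportional decline and the 15-minute Hb product comparison, report an analysis that excludes off-protocol episodes under the episode-level definition already in SAP VIII.A. Place it beside the as-assigned FAS analysis.
2. State which 15-minute Hb is analysed. Where an off-protocol unit was supplementary, use the value drawn before that unit, so that a poor MIR result is not deleted. Write this as an explicit exception to the episode-level exclusion. It cannot rescue proportional decline, because the interval then contains conventional cells.
3. State whether *product type* in the success-rate model means product received or product assigned.
4. Keep RBC mass infused as assigned.

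The cost is wording and one extra set of tables, with no new data. The exclusion analysis loses some episodes and conditions on a post-randomization event; the as-assigned analysis kept beside it covers that weakness. SAP I.B lets a blinded statistician without access to the data amend the SAP before database lock. Settling the rule then avoids choosing it after the off-protocol patterns are known.

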21.8 Sample Size Rationale

Data from the IMPROVE II study were available to obtain information on normalized Hb AUC associated with RBCs derived from Mirasol-treated WB as well as from untreated WB. Pairwise differences in the natural log-transform of normalized Hb AUC from treatment and control were used to obtain estimates required for determining the sample size needed for this study.

The mean difference in log-transformed Hb AUC values suggests a reduction of 16.7% resulting from the use of RBCs derived from Mirasol-treated WB. The sample variance of within subject differences is 0.015412. The estimate of the within subject variance required for the 2x2 crossover design is one-half of the variance of within subject differences (0.007706).

The primary hypothesis is that RBCs derived from Mirasol-treated WB are not inferior to conventional, untreated RBCs with respect to Hb AUC. Assuming a within subject variance of 0.007706 and a 16.7% reduction in Hb AUC, approximately 77 subjects are needed to obtain at least 80% power to show the decrease in Hb AUC from RBCs derived from Mirasol-treated WB is not more than 20% of the Hb AUC less from conventional untreated RBCs assuming a 1 tailed type 1 error rate of 2.5%. Algebraically if $\ln(\mu_M)$ is the mean of the natural log-transformed Hb AUC for RBCs derived from Mirasol-treated WB and $\ln(\mu_C)$ is the mean of the natural log-transformed Hb AUC for conventional untreated RBCs, the sample size is calculated to detect an alternative hypothesis versus a null hypothesis stated as:

$$H_0 : \ln(\mu_M) - \ln(\mu_C) \leq -22.3\% \text{ versus } H_a : \ln(\mu_M) - \ln(\mu_C) > -22.3\%$$

In the original scale (indicated by *), the above hypotheses translate to:

$$H_0 : \frac{\mu_M^*}{\mu_C^*} \leq 0.80 \text{ versus } H_a : \frac{\mu_M^*}{\mu_C^*} > 0.80$$

Assuming a potential 20% discontinuation rate, approximately 97 patients may be enrolled.

The sample size was calculated using SAS 9.3 proc power for paired two samples t-test with option for finding difference with the null difference at the non-inferiority margin of -0.2231 (corresponding to 20% non-inferiority margin at the original scale), true mean of -0.1839

(corresponding to 16.7% observed decrease in IMPROVE II), and correlation of 0.35. Should the correlation be higher, the proposed sample size will have higher power for the non-inferiority test.

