5 CLINICAL TRIAL EXPERIENCE

There have been 3 completed clinical trials of the Mirasol System for WB, overviews of the results are provided below.

The first 2 clinical studies evaluated radiolabeled recovery and survival of autologous RBCs derived from Mirasol-treated fresh WB and reinfused in healthy adult subjects.

In the third clinical study, the efficacy of the Mirasol System for WB was evaluated for reducing the transfusion transmission of malaria by transfusion of Mirasol-treated WB. Additional measured endpoints included bacteria reduction, hematological parameters, biochemistry parameters, and coagulation parameters.

For detailed information about clinical trial experience, refer to the current Mirasol System for WB IB.

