7 OBJECTIVES

7.1 Primary Objective

The primary objective of this clinical study is to determine if percent survival of RBCs derived from Mirasol-treated WB is non-inferior to conventional RBCs when transfused into patients requiring chronic RBC transfusion support.

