19.3.3 Risk of Increased Transfusion Frequency

The recovery and survival in vivo studies have demonstrated that compared to conventional untreated RBCs, RBCs derived from Mirasol-treated WB have reduced recovery, although still within acceptable therapeutic ranges. Specifically, the mean recovery of Mirasol-treated RBCs was 82.5% compared with 91.7% for untreated RBCs. The RBC area under the curve (RBC AUC), a measure of RBC survival, was 16.7% lower in transfused Mirasol-treated RBCs. Because of these differences, patients receiving RBCs derived from Mirasol-treated WB may require more frequent RBC transfusions and/or more units of RBCs per transfusion as compared to conventional RBCs. Transfusion frequency will be evaluated in this study to determine if there

is an increase for subjects receiving RBCs derived from Mirasol-treated WB when compared to conventional RBCs.

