21.7.1 Endpoint Measures

21.7.1.1 Primary Endpoint

The primary endpoint is normalized Hb AUC as a measure of the percent surviving RBCs. The Hb AUC is calculated using the trapezoidal method on normalized Hb. The normalization is accomplished by dividing all posttransfusion Hb values by the 15-minute posttransfusion Hb level. The ratio is expressed as a percentage. A natural log-transform of the observed normalized Hb AUC will be utilized.

The Hb will be collected within 1 hour before transfusion, 15 (+ 5) minutes, 24 ± 6 hours, and 7 days after transfusion and at the end of study treatment follow-up. The transformed Hb AUC values from the first 2 transfusion episodes after the 50 day wash-in for each period will be used for analysis. If only a single Hb AUC value is available after the wash-in for an individual period, that single value will be used for analysis.

If a patient randomized to receive RBCs derived from Mirasol-treated WB in a particular period receives 2 successive off-protocol transfusions (ie, untreated RBCs) after completing the 50 day wash-in period, the primary endpoint for that period will be excluded from the analysis. If only 1 of the 2 successive transfusions after the 50 day wash-in period is per protocol, only the primary endpoint associated with the per protocol transfusion will be analyzed.

The primary analysis will use a mixed effect repeated measures model on the log-transformed data to assess differences between treatments using the FAS. A random subject-level effect will be used to accommodate dependence in responses within subjects over time. Fixed main effect terms for period and carry-over will be modeled along with treatment, where Mirasol-treated WB is coded 1 and conventional treatment is 0. A one-sided 97.5% confidence interval for treatment differences will be used to test the primary hypothesis that the normalized Hb AUC as a measure of RBC survival derived from Mirasol-treated WB is non-inferior to normalized Hb AUC after transfusion of conventional untreated RBCs. Assuming a non-inferiority margin of 20% (at the original scale), the use of RBCs derived from Mirasol-treated WB will be declared non-inferior to conventional, untreated RBCs if the lower limit of the one-sided confidence interval for the treatment effect (RBCs derived from Mirasol-treated WB mean minus conventional) is greater than $\ln(0.80) = -0.2231$.

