## **II. Protocol Objectives**

### **A. Primary**

- To determine if percent survival of RBCs derived from Mirasol-treated whole blood (WB) is non-inferior to conventional RBCs when transfused into patients requiring chronic RBC transfusion support.

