## C. Sample Size Estimation

Data from the IMPROVE II study were available to obtain information on normalized Hb AUC associated with RBCs derived from Mirasol-treated WB as well as from untreated WB. Pairwise differences in the natural log-transform of normalized Hb AUC from treatment and control were used to obtain estimates required for determining the sample size needed for this study.

The mean difference in log-transformed Hb AUC values suggests a reduction of 16.7% resulting from the use of MIR RBCs. The sample variance of within subject differences is 0.015412. The estimate of the within subject variance required for the 2x2 crossover design is one-half of the variance of within subject differences (0.007706).

The primary hypothesis is that RBCs derived from Mirasol-treated WB are not inferior to conventional, untreated RBCs with respect to normalized Hb AUC. Assuming a within subject variance of 0.007706 and a 16.7% reduction in normalized Hb AUC, approximately 77 subjects are needed to obtain at least 80% power to show the decrease in normalized Hb AUC from RBCs derived from Mirasol-treated WB is not more than 20% of the normalized Hb AUC from conventional untreated RBCs assuming a 1 tailed type 1 error rate of 2.5%. Algebraically if  $\ln(\mu_M)$  is the mean of the natural log-transformed Hb AUC for MIR RBCs and  $\ln(\mu_C)$  is the mean of the natural log-transformed Hb AUC for REF RBCs, the sample size is calculated to detect an alternative hypothesis versus a null hypothesis stated as:

$$H_0 : \ln(\mu_M) - \ln(\mu_C) \leq -22.3\% \text{ versus } H_a : \ln(\mu_M) - \ln(\mu_C) > -22.3\%$$

In the original scale (indicated by \*), the above hypotheses translate to:

$$H_0 : \frac{\mu_M^*}{\mu_C^*} \leq 0.80 \text{ versus } H_a : \frac{\mu_M^*}{\mu_C^*} > 0.80$$

Assuming a potential 20% discontinuation rate, approximately 97 patients may be enrolled.

The sample size was calculated using SAS 9.3 proc power for paired two samples t-test with option for finding difference with the null difference at the non-inferiority margin of -0.2231 (corresponding to 20% non-inferiority margin at the original scale), true mean of -0.1839 (corresponding to 16.7% observed

decrease in IMPROVE II), and correlation of 0.35. Should the correlation be higher, the proposed sample size will have higher power for the non-inferiority test.

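### The 16.7% effect and variance behind the sample size are labelled-cell survival figures, not normalized Hb AUC, so at equal transfusion intervals a ratio above 0.80 does not by itself show percent RBC survival within 20% of conventional

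*Protocol*

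**What the plan says.** The primary objective in Protocol 7.1 is "to determine if percent survival of RBCs derived from Mirasol-treated WB is non-inferior to conventional RBCs"; SAP II.A repeats it. The endpoint that serves this objective is built from the patient's own Hb. Protocol 21.7.1.1 states: "The normalization is accomplished by dividing all posttransfusion Hb values by the 15-minute posttransfusion Hb level". SAP VIII.A uses the same normalization and takes a trapezoidal AUC from the 15-minute value to the next pre-transfusion value.

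Protocol 21.8 and SAP IV.C take the planning effect (16.7% reduction, true log mean -0.1839) and the variance of within-subject differences (0.015412) from IMPROVE II. Both call these normalized Hb AUC data. The Protocol wording is "Data from the IMPROVE II study were available to obtain information on normalized Hb AUC associated with RBCs derived from Mirasol-treated WB"; the SAP wording is "Data from the IMPROVE II study were available to obtain information on normalized Hb AUC".

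Elsewhere the Protocol describes that study differently. Section 5 says the first two clinical studies, of which IMPROVE II is the second, "evaluated radiolabeled recovery and survival of autologous RBCs derived from Mirasol-treated fresh WB" in healthy adults. Section 5.2 gives the AUC of RBC survival as about 83% of control. Section 19.3.3 states: "The RBC area under the curve (RBC AUC), a measure of RBC survival, was 16.7% lower in transfused Mirasol-treated RBCs".

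**The concern.** A labelled-cell AUC follows only the reinfused cells. Whole-patient Hb pools the new cells with cells surviving from earlier transfusions and any that the patient makes, and each curve stops after 2-4 weeks. A given survival loss therefore need not produce the same proportional change in the two AUCs.

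Two things depend on the label. The sample size section presents a true effect just inside the margin (-0.1839 against -0.2231) and about 80% power; both statements belong to the labelled-cell scale. The primary objective is worded as percent survival, so a lower limit above 0.80 would be read as survival within 20% of conventional. If the Hb scale compresses survival differences, that reading is too strong. Section 19.3.3 itself warns that the reduced recovery and survival may mean more transfusions, so the survival reading matters.

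**Working it through.** **The plan's own figure.** Paired t-test, one-sided 2.5%, variance of differences 0.015412, margin ln(0.80) = -0.2231. With true mean ln(0.833) = -0.1827, power at n = 77 is 80.5%. With the printed -0.1839 (a 16.8% reduction), power at 77 is about 78% and 81 are needed. 77/(1 - 0.20) is about 97 enrolled. The stated N therefore follows from these inputs; the question is what the inputs measure.

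**Is 16.7% the size of a labelled-cell result?** Sections 5.2 and 19.3.3 give recovery of 82.5% (Mirasol) and 91.7% (control), and linear survival of 60.49 and 81.57 days. With linear loss, AUC to day L = recovery x (L - L²/(2 x survival)). At L = 28:
- Mirasol: 0.825 x (28 - 6.48) = 17.75
- Control: 0.917 x (28 - 4.81) = 21.27
- Ratio: 0.835, close to the reported 0.833

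**Bound on conventional Hb loss.** Inputs:
- exclusion 1: 200 mL/kg/year (Protocol 11.3)
- volume formula: mL = Hb rise x kg x 3/Hct (Protocol 14.3)
- unit Hct: about 57% (Table 19-5)

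At steady state Hb loss equals Hb given: 200 x 0.57/3 = 38 g/dL per year, and 38/365.25 = 0.104 g/dL/day. That is 1.46, 2.18 and 2.91 g/dL over 14, 21 and 28 days.

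**IMPROVE II loss relative to control.** (0.917 x 81.57)/(0.825 x 60.49) = 74.80/49.90 = 1.50-fold.

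**Conversion at equal intervals.** Let x be the fractional fall on conventional RBCs over the interval. With a straight-line fall, mean normalized Hb is 1 - x/2 on conventional and 1 - 1.50x/2 on Mirasol. The documents give no 15-minute Hb, so 10-14 g/dL is an assumption. Setting (1 - kx/2)/(1 - x/2) = 0.80 gives the loss multiple at the margin, k = 0.4/x + 0.8.

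| Interval, 15-min Hb | x | REF mean | MIR mean | Ratio | k at 0.80 |
|---|---|---|---|---|---|
| 14 d, 14 g/dL | 0.104 | 0.948 | 0.922 | 0.973 | 4.64 |
| 21 d, 12 g/dL | 0.182 | 0.909 | 0.864 | 0.950 | 3.00 |
| 28 d, 10 g/dL | 0.291 | 0.854 | 0.782 | 0.915 | 2.17 |

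The first and last rows are the extremes of the range. In terms of recovery x lifespan, the margin corresponds to 1/4.64 = 22% up to 1/2.17 = 46% of control, against 1/1.50 = 67% in IMPROVE II. A crossover simulation with a 50-day wash-in and the four-point trapezoid, calibrated to the same conventional fall, gave ratios of 0.929-0.970.

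**Sensitivity to how the cap is read.** The above takes the cap as volume of RBC product, which is what the volume formula returns. Read as pure red-cell volume, the bound is 200/3/365.25 = 0.183 g/dL/day. The ratio range becomes 0.83-0.95 and k becomes 1.6-3.0. Only the 28-day, 10 g/dL corner then matches the planned 0.83.

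**Unequal intervals.** The AUC is not divided by interval length. At 12 g/dL, suppose conventional stays at 21 days and Mirasol shortens to 18. The Mirasol mean is 1 - 1.50 x 0.104 x 18/(2 x 12) = 0.883, and the AUC ratio is (18 x 0.883)/(21 x 0.909) = 0.83, against 0.95 at equal intervals.

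**The case against.** **The endpoint is a declared choice.** Section 6 says there are no accepted standards for judging RBC efficacy and gives a reason for Hb AUC. The 50-day wash-in is meant to fill the circulation with the assigned product, so older transfused cells are partly the intended measurement. This stands as a defence of the endpoint. It does not defend the label on the planning figures or a conclusion worded as survival.

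**Equal intervals are not guaranteed.** Physicians set volume and frequency (Protocol 10.1), and 19.3.3 anticipates more frequent transfusion on Mirasol. As the working shows, a modest shortening can undo the compression. This stands, and it is why the conversion is conditional. It also means a reader should not infer that the primary test is lenient overall; the documents do not settle that.

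**Severe-anaemia scenarios overstate the case.** With no non-transfused Hb and a 13 g/dL start, a reader might infer that 0.80 would pass Mirasol cells living only 39-51 days, or 47-62% of conventional. The documents do not support those figures for this trial. The model implies a conventional requirement of about 470-550 mL/kg/year against the cap of 200. At 28 days it also gives a ratio of 0.84, so it shows almost no compression there.

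**Much of the remedy is already planned.** SAP VIII.C models proportional decline with a 95% CI and adds un-normalized Hb AUC. This is true, but the latter pools the same cells. Proportional decline should not be promoted to a survival measure either. In the same uncapped model its MIR/REF ratio moves from 1.35 through 1.30 to 1.26 as the interval lengthens from 14 to 28 days, against 1.50 for recovery x lifespan.

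**Conclusion.** The point holds. Protocol 21.8 and SAP IV.C attach an Hb label to a labelled-cell effect and variance, and neither document converts the scale or justifies 20% on it. At equal intervals, with a 15-minute Hb of 10-14 g/dL, the cap read as product volume and a straight-line fall, the IMPROVE II loss corresponds to a ratio of about 0.92-0.97. The 0.80 margin is reached only at a 2.2- to 4.6-fold loss rate. A ratio above 0.80 therefore does not by itself show percent survival within 20% of conventional.

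The size rests on the assumed Hb level, the reading of the cap and equal intervals; the mislabelling rests on none of them. A reader might also infer that N = 77 is too small. This conversion does not show that, since a smaller true reduction would raise power. However, the variance also comes from the labelled-cell scale, so no Hb-scale power figure can be taken as established. The harm is to interpretation.

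**What to change.** 1. In Protocol 21.8 and SAP IV.C, state that the 16.7% and 0.015412 are labelled-RBC survival figures from IMPROVE II. Give the expected normalized Hb AUC ratio for 2-4 week intervals with its assumptions, and say that the 80% power at N = 77 applies to the labelled-cell scale.
2. In SAP VIII.B, state that meeting 0.80 supports non-inferior Hb maintenance between transfusions and is not by itself a conclusion on percent RBC survival.
3. In SAP VIII.C, report the planned proportional decline per day with its 95% CI beside the primary result, and also express it as a MIR/REF ratio of model means. Describe it as supportive evidence on the rate of Hb loss, not as the survival measure. A ratio of model means avoids logging individual declines that may be zero or negative.

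Margin, N, primary test and data collection are unchanged. The cost is wording in two documents and one extra display of an existing analysis. The downside is a narrower claim. The changes should be made before database lock.
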